Participants have been randomized to probiotic or placebo using fixed equal allocation ratios. An independent researcher/statistician at University of Bergen created a computer-generated randomization list, with the study identification number of patients, from 1 to 2000, allocated to probiotic or placebo. We have not planned for any restrictions to reduce the predictability of the randomization list. The probiotic and placebo are identical in taste and color, and produced in identical bottles. A pharmacist, who was not part of the study, was provided with the randomization list and labelled the identical bottles, numbered from 1 to 2000. This was performed before shipment to the study site. At the time of inclusion of infants in the ProRIDE study, study personnel provided the parents with consecutive, prelabelled bottles with probiotic or placebo according to the randomization list.

11. Sample size

Infant mortality rate in Tanzania was in 2018 reported at 3.8%. We do not have exact data for the Mbulu district, but we assume a similar rate of approximately 4%. Serious infections leading to hospitalization are probably equally common, but hospitalization rates may depend on available access. In the Panigrahi study, a synbiotic product was given for only seven days, and it reduced the composite outcome death and/or infection from 9.0% to 5.4% during the first two months of life. In our study, the intervention will continue for around four weeks and follow-up will continue until six months of life. We consider a similar reduction in the composite outcome death and infections leading to hospitalizations from 9.0% to 5.4%, as in the Panigrahi study, to be clinically relevant (1). To find this difference with a study power of 85% at 5% significance level a sample size of minimum 924 cases in each arm; thus 1848 infants is needed. In order to allow for drop-out we aimed to include 2000 infants. With this number of infants, we will also have sufficient power to detect a minimum of 30% reduction in ESBL-E colonization rate (from around 50% to 35%) at six months of age.

We finished recruitment of 2000 participants in January 2023 and will complete 6 months follow-up for all participants in July 2023.

12. Framework

The study will test the hypothesis of superiority of probiotic over placebo in preventing death or hospitalization during the first 6 months of life. Comparison of the proportion of participants with the primary outcome will be presented.

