13. Statistical interim analysis and stopping guidance

Interim analyses have been performed after six month follow-up of 500 and 1000 infants. The major outcomes and adverse outcomes of interest; mortality, hospitalizations and blood culture confirmed sepsis have been summarized and presented to the DSMB. Only the study statistician have had access to these results. If mortality between groups (probiotic vs placebo) at 6 weeks follow-up had been significantly different at the level of $p<0.05$ by Chi square test at assessment at these two time points of the study, the study would have been stopped. This decision had in that case to be taken by the PI of the study, in consultation with co-investigators and the DSMB. Other triggers that would call for an unscheduled DSMB review were if infant mortality or morbidity rates clearly exceed expected rates in Tanzania. Severe adverse events have also been reported consecutively to the DSMB, and the DSMB have evaluated this independently of the interim analysis.

14. Timing of final analysis

Final analysis of data will be performed after all patients have completed 6 months follow-up. This analysis will be performed on anonymized data. Blinding for investigators and patients will be maintained until the study is completed.

15. Timing of outcome assessments

The primary outcomes will be assessed at 6 months. Secondary outcomes will be assessed at 6 weeks and 6 months. Additionally, adverse events have been and will be reported to the DSMB consecutively for independent evaluation until the study is completed.

Statistical principles

16. Levels of significance, P values

Analysis results for the primary outcome will be reported as odds ratio with 95% confidence interval with P-value. The standard cut-off of $p<0.05$ will be used for statistical significance levels. For secondary outcomes we will report appropriate effects measures with 95% confidence intervals without p-values.

17. Rationale for any adjustment for multiplicity, and, if so how the type 1 error is to be controlled

Type I error will be controlled at the traditional 0.05 two-sided level for the hypothesis test. We will perform a hypothesis test only for the primary outcome and we will not need to adjust for multiple tests.

18. Confidence intervals to be reported

Odds ratios and other relevant effect-measures will be estimated in appropriate regression models and will be reported with 95% confidence intervals.

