19. Adherence and protocol deviations

Any deviations from the protocol will or have already been documented in a protocol deviation form and filed in the study master file. A SOP is in place describing the procedure for identifying non-compliances, escalation to the central team and assessment of whether a non-compliance /deviation may be a potential Serious Breach.

20. Analysis populations

The primary analysis will be an “intention to treat” analysis performed on all patients who were randomized. In addition, per protocol analysis will be performed for patients who reported to have adhered to the ingestion of the study product (probiotic or placebo), and on other subgroups of the study population.

Trial population

21. Screening data

Pregnant women in their last trimester, visited at home or attending the last antenatal care visit at HLH, will receive oral and written information about all aspects of the study before giving consent to let their future child participate in the study. Trained research assistants who speak the local language will be in charge of obtaining informed consent before recruitment.

22. Eligibility

Inclusion criteria

Healthy newborn infants with a birth weight (BW) equal or above 2.0 kg are eligible for inclusion. Newborn infants have to come from families who are long-term or permanent residents in the defined catchment area for this trial (30 km radius from HLH) in Tanzania. Parents have to be able and willing to complete study visit (including required study procedures) schedules over the six months proposed follow-up. This also includes that they, if possible, bring their child to the hospital in case of any intercurrent illness. Parents have to sign informed consent form (ICF) and have to agree that the child cannot participate in another clinical trial during the study period

Exclusion criteria

BW below 2.0 kg, refusal of informed consent and/or other health problems/illness including obvious congenital malformations

23. Recruitment

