Patients will be recruited among newborns; born at Haydom Lutheran Hospital (HLH) in North East Tanzania and out-born newborns in the surrounding area. HLH is located in the Mbulu district, at the western end of the Manyara region in the North-Central Tanzania, about 300 km south-west from regional center Arusha. The HLH catchment area consists of four administrative divisions, three districts and two regions. These are the Dongobesh and Haydom divisions in Mbulu District, the Basotu Division in Hanang District (Manyara Region), and the Nduguti Division in Iramba District (Singida Region). The hospital serves a population of more than two million people from five regions. Annually, there are more around 3900 deliveries in the hospital, and in 2018 the neonatal mortality rate in Tanzania was around 21/1000 live births.

24. Withdrawal / follow-up

Participation is based on informed voluntary consent of the parents of the child. Parents may decide that their child may withdraw at any time of the study without giving reasons or justification. Upon withdrawal, no further data will be collected. However, data recorded up until the time of withdrawal will be included in the analysis.

25. Baseline patient characteristics

Baseline data on demographic characteristics are recorded as detailed in the eCRF.

Analysis

26. Outcome definitions

Primary outcome

Prevalence (%) of the composite outcome death and/or hospitalizations at six months of age.

Secondary outcomes

- Rates (%) of ESBL-E colonization at six weeks and six months of age.
- Rates (%) of hospitalizations up to six months of age.
- Rates (%) of confirmed sepsis (blood culture-confirmed) episodes up to six months of age.
- Growth monitored by length and weight up to six months of age.
- Stool microbiota composition including resistome analysis (metagenome sequencing) at six weeks and six months of age.
- Stool metabolome composition at six weeks and six months of age.
- Stool inflammatory markers at six months of age
- Genetic characteristics of ESBL-E from colonization and clinical samples (targeted screening).
- Risk factors for death, hospitalization and sepsis.
- Primary and secondary outcomes will secondarily be performed stratified for place of delivery, ie hospital, home or primary health care facility.

27. Analysis methods

Clinical and microbiological data

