In univariate analysis, comparison of proportions will be done using Pearson's chi-squared test and comparison of means will be done using t-test or non-parametric tests as appropriate. Logistic regression will be used for multivariate analysis when assessing the relative importance of risk factors for carriage of ESBL-E and other multi-resistant bacteria.

Stool microbiota, stool metabolome and stool inflammatory markers

Stool microbiota: A Poisson generalized linear model will be used to calculate trends in the relative abundance of genera and antibiotic resistance genes in the stool microbiota. Corrections based on multiple comparisons will be performed by the Benjamini-Hochberg false discovery rate (FDR). An FDR Q value $\leq .10$ will be considered significant for any analyses with multiple comparisons. A standard P value $\leq .05$ will be considered significant for all other analyses. Alpha diversity of the gut microbiota will be assessed by calculating the Shannon Diversity index (MEGAN, v5.10.6). Multiple beta diversity metrics of

samples will be performed by using non-metrical multidimensional scaling (NMDS), based on a matrix of Bray-Curtis distances and calculated by using the vegan R package. Differences between groups will be tested by using permutational multivariate analysis on beta diversity matrices.

Stool metabolites will be identified by using mass spectral (MS) databases (e.g., MzCloud, Metlin) and standards purchased for this project. For statistical and pathway analyses, we will use web-based tool MetaboAnalyst. All MS data will be submitted to and stored at the European Bioinformatics Institute repository MetaboLights. Stool inflammatory markers will be analysed with conventional statistical tools for interval data using parametric or non-parametric tests, as appropriate.

28. Missing data

Missing data for both binary and continuous variables will in the main analyses be handled as non-responses. Depending on the degree of missingness, we will perform supplementary analyses with multiple imputation of missing values to assess the possibility that the missing data may introduce bias.

29. Statistical software

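### Does the undefined term for missing data in SAP section 28 leave the primary result open to choice?

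*SAP*

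**What the plan says.** The primary outcome (SAP section 26) is "Prevalence (%) of the composite outcome death and/or hospitalizations at six months of age". Section 16 sets the reporting: "Analysis results for the primary outcome will be reported as odds ratio with 95% confidence interval with P-value". Section 17 makes this the only hypothesis test. For secondary outcomes, section 16 says: "For secondary outcomes we will report appropriate effects measures with 95% confidence intervals without p-values".

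On missing values, section 28 says: "Missing data for both binary and continuous variables will in the main analyses be handled as non-responses". It then offers multiple imputation as a supplementary check for bias, depending on how much is missing. Section 29 names R software for imputing by group. Neither document defines the term, and protocol section 7.0 has no missing-data rule.

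Three other places bear on it:
- Section 20 makes the primary analysis intention to treat, "performed on all patients who were randomized".
- Section 24 stops data collection at withdrawal but keeps what was recorded before it.
- Section 11 explains the margin in the sample size: "In order to allow for drop-out we aimed to include 2000 infants".

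**The concern.** In trials where the outcome is a benefit, handling a missing value as non-response usually means counting it as a failure. Here the outcome is death or hospitalisation, so the term has no obvious direction. Three readings are possible for an infant with no recorded event and unknown status at six months: (a) left out, (b) counted as event-free, (c) counted as an event.

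Reading (a) appears to clash with an analysis of all randomised infants. Reading (c) would add the same block of artificial events to both arms if loss is equal, pulling the odds ratio towards 1. If loss is unequal it would create a difference of its own. The rule governs the trial's only test, and for length, weight and stool markers it supplies no value at all. The trigger for imputation is also left to judgement.

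**Working it through.** **Inputs.** Rates p1 = 9.0% (placebo) and p2 = 5.4% (probiotic), two-sided 5%, 85% power, 924 per arm needed and 2000 recruited (SAP sections 11 and 17). No loss rate is stated. The margin implies 1 − 1848/2000 = 7.6%, used here as an assumption with a range around it.

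**The plan's own figure.** With pooled variance and mean rate 0.072:

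n = [1.960·√(2·0.072·0.928) + 1.036·√(0.0819 + 0.0511)]² / 0.036² = 924.2 per arm.

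This agrees with the stated 924. Power at 924 is Φ[(0.036 − 1.960·0.01203)/0.01200] = Φ(1.036) = 85.0%.

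**The three readings, equal loss m, 1000 randomised per arm.** (a) n = 1000(1−m), rates p. (b) n = 1000, rates p(1−m). (c) n = 1000, rates p(1−m) + m. For (c) at 7.6%: 0.09·0.924 + 0.076 = 15.9% and 0.054·0.924 + 0.076 = 12.6%.

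| Loss per arm | (a) OR, power | (b) OR, power | (c) OR, power | (c) p at expected counts |
|---|---|---|---|---|
| 2% | 0.577, 87.0% | 0.578, 86.9% | 0.648, 78.5% | 0.006 |
| 5% | 0.577, 85.9% | 0.578, 85.8% | 0.719, 65.8% | 0.018 |
| 7.6% | 0.577, 85.0% | 0.579, 84.8% | 0.761, 56.7% | 0.033 |
| 10% | 0.577, 84.1% | 0.580, 83.8% | 0.790, 49.7% | 0.051 |

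In 400,000 simulated trials at 7.6% loss, (a) and (b) disagreed on significance in 1.4%, and (a) and (c) in 32%. With balanced loss the choice between (a) and (b) hardly matters to the test. It shows mainly in the percentages promised in section 12 ("Comparison of the proportion of participants with the primary outcome will be presented"): 9.0% and 5.4% against 8.3% and 5.0%.

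**Unequal loss, same true rates.**

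| Loss, placebo / probiotic | (a) OR, power | (b) OR, power | (c) OR |
|---|---|---|---|
| 5% / 10% | 0.577, 85% | 0.546, 91% | 1.11 |
| 10% / 5% | 0.577, 85% | 0.614, 76% | 0.51 |

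Readings (a) and (b) now disagree on significance in 6.0% and 8.9% of simulated trials. The estimates stay on the same side of 1, and at expected counts both are significant.

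**Which reading the text supports.** The sentence covers binary and continuous variables together. A weight or a stool marker cannot be set to an event, whereas leaving a missing value out works for both types. Section 11 recruits extra infants so that 924 per arm remain, which treats lost infants as not evaluable. Imputation offered as a check on bias from missing data is what one adds to an observed-case analysis. All three point away from (c).

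**Would imputation as the primary method help?** Lost infants were imputed from their own arm's rate with no useful predictors (7.6% loss, 40,000 trials, 20 imputations each). Power was 84.9% against 85.0%, and the geometric mean odds ratio was 0.576 for both methods. For one example, 83/924 against 57/924 (observed-case p = 0.022), 200 repeats with 50 imputations gave p from 0.017 to 0.032.

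**The case for a change.** The strongest case is that no sentence rules out (c), and its effect would be large. In the example above, with 76 lost per arm, p moves from 0.022 (excluded) or 0.023 (non-event) to 0.100. About 1.7% loss per arm is enough to bring power under (c) below 80%. With unequal loss and no true effect (9.0% in both arms, 5% against 10% lost), (c) alone would produce an odds ratio of 1.41 with p = 0.005. A defining sentence costs almost nothing, and without one the choice could be made once missingness is known.

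Part of this stands. The definition is absent, and (a) and (b) are not interchangeable when loss differs by arm. The rest is weaker:

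- The example's observed odds ratio is 0.67, a smaller effect than planned. At the planning rates and 7.6% loss, even (c) stays significant at expected counts (p = 0.033); significance goes only near 10%.
- The 7.6% is a recruitment margin, not a forecast of missing outcomes. Protocol section 3.8.2 provides a form for unscheduled visits and separate recording of deaths and hospitalisations, so loss on the primary outcome may be lower.
- The clash with section 20 is a tension. That section contrasts intention to treat with per protocol, so it settles who is analysed rather than how an unknown outcome is scored.
- The artefacts that (c) creates are themselves a reason why an analyst would not choose it for a harm outcome.
- Growth and markers need no assigned value in an observed-case analysis, and they carry no p-value.
- On timing, section 14 says: "Blinding for investigators and patients will be maintained until the study is completed". This limits choice informed by allocation, though section 13 gave the study statistician access to interim results.

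**Conclusion.** No change to the plan follows. The wording is loose, but the two readings a statistician would take from it lead to nearly the same test: odds ratios of 0.577 and 0.579 and power of 85.0% and 84.8% at 7.6% balanced loss. At 5% against 10% loss the difference is modest: 0.577 against 0.546 or 0.614. The damaging reading (0.761, 56.7% power) does not fit the sentence it would have to come from. Promoting multiple imputation to the primary analysis would reverse the SAP's own order, show no gain in power or estimate, and add simulation noise to the only hypothesis test. Extra bounding analyses would be a sensitivity request on which statisticians may differ.

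This rests on the planning rates, 1000 infants per arm, loss unrelated to outcome within each arm, and an inferred loss rate. Heavy loss, or loss that depends on the unseen outcome, would matter under any of the readings. The supplementary imputation in section 28 is meant to examine bias from missing data, though it cannot by itself cure loss of the second kind.
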